	UCN2, UCN3: Urocortins 2 and 3

PROTOCOL SYNOPSIS

Title	InTiME: Pilot Phase 1/2, Open-Label, Clinical Trial to I nvestigate CT38 in the Treatment of M yalgic E ncephalomyelitis / Chronic Fatigue Syndrome
Indication	Myalgic encephalomyelitis/chronic fatigue syndrome (ME/CFS)
Protocol Number	ME-101p
Study Sponsor	[name] Bateman Horne Center
Principal Investigator	[name] Bateman Horne Center
Study Sites	The study will be conducted at a single center in the US.
Clinical Phase	1/2
Study Period	Planned duration of the study (for each patient): 9 weeks Planned recruitment period: 12 weeks
Objectives	To evaluate the efficacy of CT38 in the treatment of ME/CFS, based on changes in patient-reported symptoms (e.g., fatigue, pain, sleep, cognition, orthostatic intolerance, temperature, flu-like, headaches or sensitivities, shortness of breath, gastrointestinal, urination, anxiety, depression), hours of upright activity, functional capacity (activity, sleep quality, energy expenditure, heart rate), and general health status (global change, vitals) To evaluate the effect of CT38 on orthostatic intolerance To gain preliminary insights on the safety and tolerability of CT38 in ME/CFS patients
Study Design	Single-center, open-label, 3-arm Phase 1/2 clinical trial The study is comprised of a screening and recruitment period, a 4-week pre-treatment assessment period, a 1-week interventional treatment period, and a 4-week post-treatment assessment period
Duration of Treatment	3.5 hours at each of Visits 3, 4 and 4b (total of 10.5 hours)
Number of Patients	Total of 18, with at least 3 in each of D1 and D2 dose groups (sequentially-dosed) and the remainder allocated to a final dose determined by D1/D2 tolerability
Study Agent	CT38s, a peptide agonist selective for the corticotropin-releasing factor receptor subtype 2, delivered by subcutaneous administration

Dosing	
The study will utilize a continuous subcutaneous infusion at 3 dose levels. The planned Low-dose delivered ~0.8 µg/kg over 3.5 hours (on 2 separate treatment days), was associated with clinically significant hemodynamic changes, and is closed out.
 
The revised doses will deliver 0.11 and 0.35 µg/kg by continuous subcutaneous infusion.

Inclusion Criteria	
Able to read, understand and voluntarily sign the informed consent form
 
18-60YO male or female, meeting Fukuda, Canadian and IOM criteria for ME/CFS, and relatively stable state of illness for the past 3 months
 
Agree to refrain from taking medications that would affect assessment of the effectiveness of study medication for the duration of the study
 
Living at an altitude between 3,500 and 5,500 feet above sea level for the past 1 year
 
Availability for the duration of the study
 
Have mobile (smart) phone and access to the internet

Exclusion Criteria	
Alternate medical or psychiatric illness that explains ME/CFS symptoms
 
Active or uncontrolled co-morbidities (including depression, untreated endocrine diagnoses, recent acute infection, the presence of a supra-ventricular tachycardia or ventricular tachycardia, severe baseline hypotension, etc), which in the opinion of the PI may interfere with the ability of the patient to participate in the study
 
Pregnancy, or while breast feeding
 
Cigarette smoker or former smoker who has smoked within 6 months of the study
 
Renal impairment, Body Mass Index > 35, or evidence of substance abuse
 
Participating in another clinical treatment trial, or symptoms improving as a result of treatment intervention in the past 3 months
 
Current treatment with medications that interact with the 5HT, norepinephrine, dopamine or cortisol pathways
 
Treatment with short-term antivirals/antibiotics within 4 weeks, Rituximab™ within 6 months, or anti-retrovirals within 1 year, of entry into the trial.

Efficacy Evaluation	
Primary Endpoint: The change in patient-reported daily symptom levels
 
Secondary Endpoints, include a determination of treatment-related effects on functional capacity, orthostatic intolerance and general health status

Safety Evaluation	
Adverse events occurring after patient enrollment through to the final visit to the clinic, will be assessed and recorded. Serious adverse events deemed related to study treatment will be followed until resolution or stabilization of the event.

SCHEMATIC OF STUDY DESIGN

1.1. Introduction

1.1.1. Myalgic Encephalomyelitis / Chronic Fatigue Syndrome (ME/CFS)

Myalgic encephalomyelitis/chronic fatigue syndrome (ME/CFS), also known as systemic exertion intolerance disease, is a complex disorder that may be triggered by infection or other stressors (e.g., emotional or physical trauma, immune activation, chemical exposures). Its hallmark is a reduced capacity for physical and mental activity manifest as profound fatigue along with a cascade of debilitating symptoms (including pain, cognitive dysfunction, orthostatic intolerance, sensitivities, and irregularities of the autonomic, immune and metabolic systems) that worsen with activity (referred to as post-exertional malaise or PEM), are not improved by sleep, and can persist for years. ME/CFS affects up to 2.5 million Americans and results in annual direct and indirect economic costs between \$17 and 24 billion in the US. There are no approved therapeutics for ME/CFS. Patients are often unable to handle the activities of daily living and experience a loss of career and a very poor quality of life [IOM 2015].

The etiology of ME/CFS is unknown. The disease is often thought of as a stress- and/or neuroendocrine-related complication, with patients showing abnormalities of the hypothalamic-pituitary-adrenal (HPA) axis and of the immune, metabolic, norepinephrine and serotonin (5HT) systems. In young animals, intense stress can bring about an up-regulation and relocation of the corticotropin-releasing factor receptor subtype 2 (CRF₂) to the membranes of 5HT neurons in the raphe nuclei (i.e., the source of 5HT in the brain and cord) and limbic system, which can persist into adulthood. In this configuration, a minor stress stimulates (rather than inhibits) the release of 5HT from the raphe nuclei and throughout the limbic system, and the excess of 5HT leads to a desensitization of the 5HT_{1A} autoreceptor and compromised 5HT regulation [Wood 2013, Neufeld-Cohen 2012, Lukkes 2009a, Lukkes 2009b, Waselus 2009, Lukkes 2008]. Cortene Inc. (see below) has postulated that ME/CFS results from such CRF₂ up-regulation and relocation, and relative to healthy subjects, ME/CFS patients show increased brain and/or hypothalamic 5HT [Dinan 1997, Sharpe 1997, Bearn 1995, Cleare 1995, Bakheit 1992], 5HT_{1A} desensitization [Cleare 2005] and higher positivity for 5HT serum antibodies that correlate with increased physio-somatic symptom scores (muscle pain, autonomic symptoms, flu-like malaise) and sadness [Maes 2013]. This hypothesis of a CRF₂ maladaptation, resulting in an excess of 5HT under subsequent stress, comprehensively explains the symptoms and anomalies of ME/CFS. However, in the absence of an animal model of ME/CFS, the hypothesis can only be investigated in humans.

1.1.2. Investigational Agent

CT38 [proprietary data redacted] is a custom [proprietary data redacted] CRF₂-selective, peptide agonist...[proprietary data redacted] comprised of naturally-occurring amino acids, and is easily synthesized [Investigator's Brochure or IB].

CT38 was previously filed under investigational new drug (IND) application [proprietary data redacted], with the Division of Metabolism and Endocrine Drug Products at the Food and Drug Administration (FDA), to evaluate its effect in preventing muscle atrophy and wasting associated with various disease conditions. Completed studies included all the pre-IND studies (necessary for an acute indication) as well as a Phase 1 clinical trial in healthy humans. Full study reports were submitted to the FDA under IND [proprietary data redacted], and there were no outstanding issues when the IND was voluntarily withdrawn in 2008 (for strategic reasons unrelated to CT38). Cortene Inc. ("Cortene") licensed CT38 along with the right of reference to IND [proprietary data redacted].

1.1.2.1. In Vitro Pharmacology

CT38, CT38s (acetate salt of CT38, [proprietary data redacted]), CT37 (backup lead, [proprietary data redacted]), UCN2 and urocortin 3 (UCN3, endogenous CRF₂-selective peptide) were evaluated for selectivity and potency against CRF₁ (via A7r5 rat aortic cell lines) and CRF₂ (via Y-79 human retinoblastoma cell lines), by measuring cyclic adenosine monophosphate (cAMP) formation after treatment with the compound of interest. CT38 was found to have a greater than 50-fold selectivity for CRF₂ over CRF₁, and comparable CRF₂ potency to UCN2 [IB].

1.1.2.2. *In Vivo Pharmacology*

In vivo, CT38, CT37 and other custom CRF₂ agonists show similar beneficial effects to UCN2 and/or UCN3, in animal models of muscle wasting (due to casting, denervation, corticosteroid excess, dystrophin-deficiency), tumor growth and metastases, inflammation, obesity, GI transit time and the cardiovascular system, specifically changes in heart rate (HR) and blood pressure (BP) [IB].

1.1.2.3. *Safety Pharmacology and Toxicology*

There is little or no binding of CT38 when tested against various receptors, transporters, ion channels and enzymes, other than CRF₁ (weakly binding at very high concentrations). CT38 does not cause QT prolongation *in vitro* (in human ether-a-go-go related gene or hERG channel and Purkinje fiber assays) and *in vivo* (rats and monkeys). *In vivo* safety pharmacology studies demonstrate that high doses of CT38, administered as CT38s by the subcutaneous (SC) route, has pharmacological effects on the central nervous system (drop in spontaneous motor activity, decreased body temperature, tremors and subdued behavior), respiratory system (decreased respiratory rate and tidal volume), cardiovascular system (tachycardia, hypotension), gastrointestinal system (decreased transit time), and renal system (enuresis and diuresis) [IB].

Toxicology studies (mouse, rat, dog, rabbit, monkey, human *in vitro*) show that CT38 (administered as CT38s by the SC route) has large safety margins with mostly mild, dose-dependent, transient and reversible effects. CT38 is not genotoxic (*in vitro* Ames and chromosome aberration assays), has no effect on corticosterone and aldosterone levels, and in 1-month repeat dose toxicology studies in rats and monkeys, there was little or no drug accumulation and no antibody formation (histology). CT38 is eliminated by renal filtration and the terminal elimination half-life ($t_{1/2,z}$) is < 2 hours [IB].

In animals, CT38 administered by SC injection (bolus) causes transient, but dose-related increases in HR and decreases in BP, similar to UCN2 and UCN3. These were shown to be much reduced under SC infusion, potentially explained by a lower maximum plasma concentration (C_{max}). However, under continuous SC infusion in rats, the complete absence of tachycardia or hypotension even at dose levels 10,000 times higher than the bolus doses that cause such HR and BP changes, suggests that continuous SC infusion induces receptor (CRF₂) endocytosis. This is consistent with studies showing that the endocytosis of CRF₂ is a function of agonist potency, concentration and duration of exposure [IB].

1.1.2.4. *Phase 1 Clinical Trial*

CT38s was administered by SC injection (bolus) in a sequential, single ascending dose, randomized, double-blind, placebo-controlled trial in healthy male subjects. There were no deaths or serious adverse events (SAEs). Adverse events (AEs) were generally mild and anticipated from CRF₂ pharmacology. Escalating dose (in $\mu\text{g}/\text{kg}$) first caused HR increases at 0.200; tachycardia (> 100 beats per minute or BPM at rest) at 0.833; and hypotension at 1.67. The only AE classified as severe was a single subject with tachycardia (160 BPM) at a dose of 1.667 $\mu\text{g}/\text{kg}$ (resolved with propranolol). The maximum tolerated dose by bolus (MTD_b) was deemed to be 0.833 $\mu\text{g}/\text{kg}$, which showed mild tachycardia without hypotension. The $t_{1/2,z}$ was 1-3 hours. CT38 was not detectable in the plasma 8 hours post-dose. All laboratory results (including cortisol levels and QTc changes) were comparable to placebo, except for white blood cell counts, which were slightly elevated in the highest dose groups, but had resolved by the following day. The clinical study report was submitted to FDA and there were no outstanding concerns when the IND was voluntarily withdrawn [IB].

1.1.2.5. *CT38 in ME/CFS*

If ME/CFS results from an up-regulation/relocation of CRF₂ and a maladapted stress response as postulated above, then prolonged receptor stimulation via a CRF₂ agonist such as CT38, could potentially induce CRF₂ endocytosis (as demonstrated by SC infusion in rats), which could be curative. In addition, CT38 and other CRF₂ agonists can modulate many of the individual abnormalities of the disease (e.g., the HPA axis, the immune system, cortisol, glucose).

There is no animal model of ME/CFS. Moreover, specific changes in CRF₂ expression on specific neurons of the raphe nuclei and limbic system, along with any resulting excess of 5HT in these neurons under

stress, cannot be measured in a live system—though such changes have been demonstrated in animal biopsies. Therefore, assuming the hypothesized etiology is correct, the only possible way to investigate effect in humans is via a clinical trial. Given that CT38 has shown virtually identical pharmacology to the endogenous CRF₂ agonists UCN2 and UCN3, both *in vitro* and *in vivo*, and has been shown to be safe and tolerable in a Phase 1 trial in healthy human subjects, the Principal Investigator (PI), [name], a clinician with expertise in the diagnosis, treatment and study of ME/CFS, plans to evaluate CT38 as a candidate therapeutic for the treatment of ME/CFS.

To date, patients have been assessed by a variety of exploratory metrics including cardio-pulmonary exercise test (CPET) and cognitive scoring (via DANA mobile software). CPET in particular was intended to be the primary endpoint in this trial. However, the pre-treatment CPETs for all 5 patients do not indicate major patient deficits relative to historical data for healthy subjects, and they do not exacerbate patient symptoms beyond normal day-to-day stressors. Post-treatment CPETs for the 3 patients tested at the D1 dose show slight improvement in CPET parameters and reduced symptom exacerbation relative to pre-treatment exacerbation, but given the constraints that CPET imposes on the overall protocol (altitude, logistics, duration), such testing is not warranted for this essentially proof-of-concept trial. Similarly, due to the lack of sensitivity to DANA cognitive testing, and the burden on subjects to complete these daily assessments, this test will no longer be performed.

Thus, the purpose of this amendment is to add an additional 3.5-hour infusion at the D1 dose, eliminate CPET testing (and associated visits to the clinic) and DANA testing, and to designate patient-reported symptom scores as the primary endpoint.

1.2. Study Objectives

This study seeks to investigate the safety, tolerability and efficacy of CT38 in the treatment of ME/CFS patients, based on the effect of CT38 on symptom levels (e.g., fatigue, pain, sleep, cognition, orthostatic intolerance, temperature, flu-like, headaches or sensitivities, shortness of breath, gastrointestinal, urination, anxiety, depression), functional capacity (activity, sleep quality, energy expenditure, HR and

hours of upright activity), and general health status (global change, HR, BP, oral temperature, respiratory rate), pre- and post-treatment.

1.2.1. **Potential Risks**

The principal risks associated with CT38 are a potential increase in HR and decrease in BP. In the remainder of this trial, CT38 will be dosed via continuous SC infusion, repeated on 3 separate days. The original protocol lowest dose-level was associated with increased HR and decreased BP. The revised dosing utilizes lower rates of infusion and lower total doses. To mitigate risks further, dosing will be sequential, commencing with the lowest dose group and escalating only in the absence of clinically important hemodynamic changes at the preceding dose-level. HR and BP will be monitored during dosing and will have to remain within an acceptable range (see below), as a prerequisite for ascending to the next dose-level.

Beyond the investigational agent itself, there are minor risks associated with needle insertion, for blood sampling or drug administration.

1.2.2. **Potential Benefits**

If the hypothesized up-regulation of CRF₂ is correct, and if the proposed treatment achieves CRF₂ endocytosis (as it likely does in rats—based upon the loss of the ability to induce effects mediated by CRF₂ stimulation), the proposed treatment could reset the receptor within the raphe nuclei and limbic system to pre-ME/CFS levels. This should reduce the sensitivity of the stress response, thereby reducing stress-induced symptom exacerbation. If the receptor remains internalized, the treatment could be curative.

1.3. **Investigational Plan**

1.3.1. **Study Design**

1.3.1.1. *Overview*

This study is a single-center, open-label, 18-patient, 3-arm Phase 1/2 clinical trial, to evaluate safety, tolerability and efficacy of CT38, administered as the acetate salt CT38s, by the SC route of administration, at up to 3 separate dose-levels, for the treatment of ME/CFS.

The study is comprised of a recruitment and screening period, enrollment (Day 1), a 4-week pre-treatment assessment period (Days 1-28), a 1-week interventional treatment period (Days 29-35) with drug infused on Days 29, 31 and 33, a 4-week post-treatment assessment period (Days 36-63), and a close-out (Day 64).

1.3.1.2. *Primary Endpoint*

The primary endpoint will be determined from a pre- and post treatment assessment of visual analog scale (VAS) scores recorded daily for each of 13 symptoms, namely: (i) fatigue; (ii) muscle/joint pain; (iii) sleep problems, e.g., un-refreshing sleep, difficulty falling or staying asleep, excessive sleepiness; (iv) cognitive problems, e.g., slow information processing, memory difficulties, inability to concentrate/focus, attention deficit; (v) orthostatic intolerance; (vi) body temperature perceptions; (vii) flu-like symptoms, e.g., sore throat, tender lymph nodes, swollen glands, fever, chills, sinus/nasal problems; (viii) headaches or sensitivities to light, sound, smell, touch, taste; (ix) shortness of breath; (x) gastrointestinal problems, e.g., nausea, stomach/abdominal pain, diarrhea; (xi) urogenital problems, e.g., frequent urination, (xii) anxiety; and (xiii) depression.

1.3.1.3. *Secondary Endpoints*

The study will also evaluate various secondary endpoints, compared across the pre- and post-treatment assessment periods, to determine treatment-related effects on activity and general health status.

Specific secondary endpoints, measured pre- and post-treatment, will include:

- An assessment of hours of upright activity, and any unusual exertion or stimulation, will be recorded at the same time each day (ideally 6-8pm).
- Exploratory measures: Assessed via Fitbit Charge 2™ (measuring activity, HR and derivative parameters including resting HR, sleep level/duration, activity level/duration, steps, calories and distance, monitored continuously and summarized daily).
- Orthostatic intolerance (OI) will be assessed at Visits 1 and 6, via of measures of HR and BP and symptomatology, while in the supine, seated and standing positions.
- General health status: Assessed via the 36-Item Short Form Survey Instrument [McHorney 1994]), and vitals (measuring HR, BP, temperature, respiratory rate) at Visits 1-6.

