1.3.3. Study Procedures

1.3.3.1. Schedule of Events

The complete schedule of study procedures is presented in Table 6.2. While efforts will be made to comply with the schedule of events and descriptions below, the precise timing may vary, except for Visit 3, Visit 4 and Visit 4b, which each must be separated by at least 48 hours and no more than 96 hours. The pre-treatment assessment period (between Visit 1 and Visit 3) and the post-treatment assessment period (between Visit 4b and Visit 6) should each be at least 4 weeks.

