1.3.3.2.5. Visit 4b (Day 33)

At Visit 4b (Day 33) patients will undergo a brief physical exam, recording vitals and any patient-recorded changes in medications or AEs. Following this, the study drug will be administered as outlined above (see Visit 2), beginning at approximately 10am.

Both before and during the infusion procedure, HR and BP will be monitored exactly as described for Visit 3, and blood samples for PK assessment will be obtained, per the schedule at Visit 3. All AEs will be assessed and recorded as well as the need for any medications. Treatment Period (Days 29-36)

Throughout the 1-week treatment period (including treatment days), patients will utilize the wearable Fitbit Charge 2™ to record activity, sleep-related data and HR, and complete the daily VAS (online), and daily hours of upright activity (online). Patients will also record any changes in medication use, any AEs and other qualitative observations (online).

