1.3.3.2.6. Post-Treatment Assessment Period (Days 36-63)

Throughout the 4-week post-treatment recovery period, patients will utilize the wearable Fitbit Charge 2™ to record activity, HR and sleep-related data, and complete the daily VAS (online), and daily hours of upright activity (online). Patients will also record any changes in medication use, any AEs and other qualitative observations (online).

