1.3.3.2.7. Visit 6 (Day 64)

At Visit 6 (Day 64), patients will undergo a final checkup, including physical examination, recording vitals and any updates to patient history. Patient will be required to complete SF-36, followed by OI testing conducted exactly as at Visit 1. All AEs will be assessed and recorded as well as the need for any medications.

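### Do the overlapping day numbers leave the post-treatment window for the daily symptom scores undefined?

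*Combined protocol and SAP*

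**What the plan says.** Section 1.3.1.1 (Overview) sets out consecutive periods: 28 pre-treatment days, then "a 1-week interventional treatment period (Days 29-35" with infusions on Days 29, 31 and 33, then "a 4-week post-treatment assessment period (Days 36-63". Section 1.3.3.2.6 repeats the last range in its title, "Post-Treatment Assessment Period (Days 36-63". At the end of section 1.3.3.2.5 a run-on heading reads "Treatment Period (Days 29-36", while the sentence below it still calls the period one week long.

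Section 1.3.3.1 (Schedule of Events) says "the precise timing may vary, except for Visit 3, Visit 4 and Visit 4b". For those three infusion visits it sets a spacing rule instead, with gaps of 48 to 96 hours. Having described the pre-treatment period as running from Visit 1 to Visit 3, it adds that "the post-treatment assessment period (between Visit 4b and Visit 6) should each be at least 4 weeks". Section 1.3.3.2.7 places the close-out on a planned day: "At Visit 6 (Day 64), patients will undergo a final checkup".

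Section 1.3.5.2 compares the pre- and post-treatment periods and leaves the choice of test to the analyst. Neither it nor section 1.3.5.1 says how a daily score is assigned to a period.

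**The concern.** Section 1.3.1.2 builds the primary endpoint on a before-and-after comparison of daily scores, so the edges of the two periods are part of the endpoint. Three things seem unsettled:

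- Day 36 is the last treatment day in one heading and the first post-treatment day in the next.
- The post-treatment period is given once by day numbers and once by visits. On the planned schedule, Days 34-35 would be post-treatment under the visit wording and treatment under the day numbers.
- The permitted spacing lets the third infusion fall on Day 36 or 37, inside the fixed range.

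The trial is open-label. If two analysts could defend different windows, one could be chosen after the scores had been seen, and an infusion day could be counted as follow-up.

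**Working it through.** **Inputs.** Planned infusions on Days 29, 31 and 33; treatment on Days 29-35 and post-treatment on Days 36-63 (section 1.3.1.1); treatment on Days 29-36 (heading in section 1.3.3.2.5); gaps of 48-96 hours, that is 2, 3 or 4 whole days, and a minimum of 4 weeks per assessment period (section 1.3.3.1); Visit 6 on Day 64 (section 1.3.3.2.7); up to 14 days for reassessment before the first infusion (section 1.3.1.6).

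**Lengths as stated.** Days 36-63: 63 - 36 + 1 = 28 days, which reproduces 4 weeks. Days 29-35: 35 - 29 + 1 = 7 days, which reproduces one week. Days 29-36: 36 - 29 + 1 = 8 days, which does not. Days 29-35 is therefore the only range that fits section 1.3.1.1, the sentence under the discrepant heading, and a post-treatment start on Day 36.

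**Day range against visit wording, planned schedule.** Visit 4b to Visit 6 is 64 - 33 = 31 days, above the 28-day minimum, and the interval contains all of Days 36-63. Both statements hold together. They conflict only if a minimum spacing between visits is read as the analysis window, which would then hold the 30 days from 34 to 63.

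**Late third infusion, Visit 3 on Day 29.** Visit 4b = 29 + g1 + g2, with each gap 2, 3 or 4 days:

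| Visit 4b | Gap pairs (of 9) | Days of 36-63 on or before last infusion | Earliest Visit 6 (Visit 4b + 28) |
|---|---|---|---|
| Day 33 | 1 | 0 | Day 61 |
| Day 34 | 2 | 0 | Day 62 |
| Day 35 | 3 | 0 | Day 63 |
| Day 36 | 2 | 1 | Day 64 |
| Day 37 | 1 | 2 | Day 65 |

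The pair counts are possibilities, not frequencies; the plan is 29/31/33. This takes the 48-96 hour limit as applying between consecutive visits. If it also covered Visit 3 to Visit 4b, only 2 + 2 days would fit and Visit 4b could only be Day 33.

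**Can the day numbers be fixed dates?** With Visit 4b on Day 37, the 4-week minimum puts Visit 6 on Day 65 or later, so Day 64 cannot be binding. After a full 14-day reassessment delay, Visit 3 is Day 29 + 14 = 43 and Visit 4b is Day 47 (43 + 4) to Day 51 (43 + 8). A literal Days 36-63 would then start 7 days before any drug was given and put 12 (47 - 36 + 1) to 16 (51 - 36 + 1) of its 28 days on or before the last infusion. Day 64 would be only 13 (64 - 51) to 17 (64 - 47) days after it, short of the minimum. The protocol's own rules therefore exclude the fixed-date reading.

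**Size.** If k of n days differ from the rest by d on average, the patient's mean moves by (k/n) x d:

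- Days 34-35 added, planned schedule: 2/30 = 0.067d
- Visit 4b on Day 36, literal window: 1/28 = 0.036d
- Visit 4b on Day 37, literal window: 2/28 = 0.071d

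The documents give no value for d. Assuming 10 to 20 points on an assumed 0-100 scale, these are 0.7 to 1.3, 0.4 to 0.7 and 0.7 to 1.4 points in that patient's mean.

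**The case for a change.** The strongest case for acting is that the statistical section is where such a rule belongs, and it has none. Symptom scores became the primary endpoint by amendment after five patients had been treated, and the trial is open-label, so an unstated boundary can in principle be chosen with the scores in view. One sentence would close it at almost no cost.

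The omission is real: no available text says that Days 36-63 move with the last infusion. But the freedom it leaves is narrow. Section 1.3.3.1 already ties both assessment periods to visits, and the alternative reading breaks the protocol's own 4-week minimum. Sections 1.3.1.2 and 1.3.5 leave far more open by listing 13 separately scored symptoms and naming neither a summary measure nor a test. Fixing one or two boundary days would barely reduce that.

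A second argument is that the two Low-dose patients and the first three D1 patients had two treatment days, and so no Visit 4b to count from. Whether their data enter the comparison cannot be judged from the available documents, which do not include the protocol version that governed them. If they are analysed, their last infusion is the natural starting point. The full schedule (Table 6.2) and the design schematic are not shown either, so neither could be checked for a window rule.

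**Conclusion.** The concern does not call for a change to the plan. It has two parts. One is a clerical slip in a heading, which the surrounding text resolves to Days 29-35. The other is an unwritten convention, that day numbers are nominal and periods follow actual infusions, which analysts would adopt because the fixed-date reading cannot be squared with the scheduling rules. With Visit 3 on Day 29, the most a literal reading could misplace is 1 or 2 of 28 diary days, and only in patients whose third infusion falls on Day 36 or 37; on the planned schedule no infusion falls inside the window. The larger displacement after a reassessment delay arises only if days before any drug were labelled post-treatment, which no analyst would do.

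This rests on reading the 48-96 hour limit as applying between consecutive visits (the stricter reading removes the late-infusion case altogether) and on treating the 4-week figure as a minimum spacing. The point sizes rest on an assumed difference and scale, and only illustrate that the effect is small.
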